### **PART B: Feasibility and Safety of a yoga program for SCD.**

Part B will assess the feasibility and safety of a yoga program for SCD. This program will comprise of 8 instructor-led group yoga sessions. We will measure psychological factors implicated in chronic pain and pain-related patient reported outcomes, and assess the feasibility of collection of these outcomes. We will also explore patient acceptability of yoga through qualitative interviews and conduct a needs assessment for the development of a smartphone app for yoga.

Participants who express interest in learning more about participating in a study of yoga in Part A will be offered this portion of the study.

Prior to enrollment in Part B, the investigators will confirm with their treating provider that the patient does not meet any exclusion criteria for the study. If any concerns are noted at this point, then patient will not be enrolled on Part B of the study, and this will be documented.

#### **Inclusion Criteria:**

- 1-SCD, any genotype
- 2-Presence of chronic pain, the presence of chronic pain will be defined based on the frequency characteristic of the AAPT criteria for chronic SCD pain, as the presence of SCD-related pain on 15 or more days of the month for the past 6 months.
- 3-Age 12-21 at time of enrollment
- 4- English speaking

#### **Exclusion Criteria:**

- 1-Daytime or nighttime oxygen requirement for hypoxia
- 2-Most Recent Hemoglobin< 5 or platelet count < 20
- 3- Known Pregnancy

- 4- Severe cognitive issues not allowing for understanding consent/ assent and instructions
- 5- History of overt stroke with significant residual motor weakness
- 6-History of recurrent syncope
- 7- Any other comorbidities or health concerns that the treating healthcare provider or investigators feel are a contra-indication for participation in the study.

The presence of the following conditions will be assessed from the medical record but are **NOT** exclusion criteria: 1) Presence of splenomegaly, 2) presence of asthma 3) presence of AVN 4) Presence of cerebral vasculopathy 5) retinopathy, 6) presence of symptomatic pulmonary HTN. The assessment of the study investigators and the treating team will determine if any of these or any other co-morbidities require for modification of or pose as potential contraindications for participation in a yoga program.

If prospective study participants are enrolled on other clinical trials that do not allow for concurrent enrollment in this study, they will not be enrolled on this study. The PI/study staff will confirm eligibility for enrollment with PI's/study staff of the respective clinical trials regarding patient eligibility for enrollment.

#### **In-person yoga sessions:**

Patients will be offered a yoga program consisting of 8 in-person instructor-led group yoga sessions. Yoga sessions are likely to be held at CHOA campuses or at ECC, depending on availability of space. Based on number of participants enrolled and participant convenience/logistical issues, study cohort may be split into 2 or more groups, but a participant may only attend a total of 8 sessions. Sessions are currently planned to be weekly, however there may be variations in schedule to accommodate situations including but not limited to major holidays, school breaks, instructor illness, etc.

- i. During the sessions, participants will be monitored by a study investigator and the yoga instructor. An investigator who is an MD familiar with care of SCD patients will be present, and a RN may also be present, both of whom will monitor patient safety at each session.
- ii. Yoga instructor is certified and have expertise in teaching yoga. Instructor will be [name]. A physical therapist ([name]), who is also a certified yoga instructor, will also assist in developing the class routine, and may be present during the session.
- iii. The yoga instructors, with the guidance of SCD clinical experts, will develop a customized set of restorative yoga poses, breathing exercises, and guided relaxation routines with consideration of needs, expectations and physical limitations of SCD.
- iv. During guided yoga sessions the yoga instructor will carefully observe the participants for any sign of discomfort or suitability. Yoga instructors will modify particular poses to be suitable for the participant. The yoga sessions will be geared towards increased incorporation of breathing techniques and mindfulness and some 'asanas' (poses). Props may be utilized for yoga poses.
- v. Timing of yoga sessions will likely be in the evenings or on weekends, to accommodate participant's ability to attend these sessions. Participants will be asked regarding their preferred times. Every effort will be made to accommodate participants.
- vi. Proposed Yoga protocol (45-60 minutes), but this may be modified as yoga instructor deems necessary to suit patients with SCD. The sequence below is only to serve as a guide, and only lists representative elements, and instructor may move around the order. The final yoga protocol may be modified in-real time per instructor discretion, and to maintain safety, based on ongoing feedback and response to classes. It is possible that some elements of the yoga sessions may change as classes progress.

- a) Opening and Pranayama (breathing exercises)
  - b) Gentle warm up
  - c) Predefined set of standing and poses
  - d) Surya (Sun), Chandra (Moon) and earth series of poses
  - e) Pranayama (Breathing exercises)
  - f) Guided relaxation or 'yoga nidra'
- vii. During, and at the end of each session, feedback will be obtained from participants as a group, and will be recorded. Future yoga sessions may be modified as necessary based on participant feedback.
- viii. Email or phone reminders for upcoming yoga sessions will be sent to participants at the email address/phone numbers provided. If participants miss or are unable to attend sessions, study staff may follow up to attempt to determine reason for non-attendance.
- ix. Study staff will also record ED visit or hospitalization that occurred in the 24 hours following the yoga session. This will be assessed 24 hours after, but prior to the start of the subsequent session.

**Assessments:**

- 1- Surveys (**2 assessments, pre and post**). The following surveys will be completed: 1) Chronic pain acceptance questionnaire 2) Tampa Scale of Kinesiophobia 3) PROMIS Pain Intensity and pain interference 4) Pain catastrophizing scale 5) Modified EXPECT questionnaire, to assess individual expectation from the yoga program. Surveys may be completed in person, or over the telephone, up to 4 weeks before the anticipated start of the yoga sessions, and up to 4 weeks after completion of the last yoga session.
- 2- Qualitative Interviews (one assessment, after completion of yoga sessions): A qualitative interview will be conducted, either in person or over the telephone. These interviews will explore participant experience with the yoga study, including perceived benefits, perceived complications/harms, challenges, barriers to successful participation, feedback on yoga classes and content, and other related themes. We will also evaluate participant beliefs and acceptability of yoga and other complementary therapies before and since the intervention. We will also assess aspects of acceptability and use of yoga as well as potential barriers as an adjunct therapy for SCD chronic pain. We will also use qualitative interviews format to assess participant interest and perceived needs in the development of a smartphone yoga app. There may be other questions that the interviewer may ask based on participant responses. Interviews may take up to 20-30 minutes. Interviews will be audio recorded and identified with the unique subject number for the study. Audio files will be transferred to the secured Hematology/Oncology share drive at Emory or CHOA. All audio recordings will be transcribed verbatim by a member of the research team. An interview script has been uploaded with the protocol, but as with all qualitative methodology, it is an iterative process, thus the interview guide may be modified based on emerging themes to better understand those themes.
- 3- We will review medical records for demographic and clinical characteristics as described earlier in the protocol.
- 4- Pain diary (2 assessments, pre and post): Participants will complete a multi-dimensional pain diary (MDP diary) for up to one week prior to and following the period of in-person yoga sessions. The pain diary is accessible via a password protected website, which is also currently used to collect pain data for other large clinical trials in SCD. Data entry will occur two times per day, morning and evening and will take less than 3 minutes to fill out at each time point. The diary can be completed up to 4 weeks prior to the anticipated start of the yoga program, and may be started up to 4 weeks following the completion of the last yoga session.

- 5- We will also obtain demographic information from patient/family including but not limited to age, sex, race, ethnicity, family income, insurance status, parent and child education status, family composition and parent marital status, religious affiliation, availability of transportation and distance from the proposed yoga site. As with Part A, if participants indicate they have previously practiced yoga, we will also gather the following: number of months/years' yoga has been practiced, frequency of practice and time of most recent practice of yoga. This would already have been gathered at the start of Part A but may be collected again if necessary.
- 6- Study staff may send email or phone reminders for completion of study assessments, and may follow up to obtain completed study assessments.
- 7- We will also follow healthcare utilization for pain during and up to 6 months after completion of the yoga program.

After the sessions have ended, and the participant has attended at least one session, all surveys will be repeated and a qualitative interview will be conducted to evaluate participant acceptability and perceived benefits/risks of yoga, as well as the perceived needs in the design of a smart-phone accessible yoga app; as described above.

The goal will be to obtain these assessments within one month prior to the planned start of Part B, and within one month of completion of the last yoga session.

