## **AIMS:**

### **Aim 1. Acceptability, feasibility and safety of a yoga program for chronic pain in SCD.**

We will assess the acceptability of yoga for chronic pain in SCD. We will also assess the feasibility and safety of a yoga program for adolescents with SCD and chronic pain.

**Rationale:** Yoga content customized for patients with SCD chronic pain, is currently not available for patients. We propose for the first time to develop routines with consideration of needs, expectations and physical limitations of SCD. The overall acceptability, feasibility and safety of such a program in SCD is yet to be studied, though data from other chronic painful and inflammatory conditions do not suggest safety concerns.

**Hypotheses:** 1a) We hypothesize that more than >50% of those with chronic pain approached to complete a survey of their attitudes and practices related to yoga, would be willing to complete a survey. 1b) At least 50% of adolescent SCD patients with chronic pain offered participation in a yoga program through in-person yoga sessions will agree to participate in the yoga program 1c) At least 80% of participants enrolled in the in-person yoga program will be

able to attend at least 6 of 8 in-person yoga sessions. 1d) Fewer than 30% of participants will have an ED visit or hospitalization for pain within 24 hours of completion of a yoga session.

**Aim 2: Feasibility of collection of psychological and patient-reported outcomes in a study of yoga for chronic pain in SCD.**

**Rationale:** Yoga content tailored and customized for patients with SCD chronic pain, is currently not available for patients. We propose for the first time to develop routines with consideration of individual needs, expectations and physical limitations. In addition to aims in Aim 1, we propose to measure health outcomes and psychological characteristics pre- and post- the yoga program, with a goal to determine the feasibility of collection of these outcomes in a larger study. Since our sample size is small, and this is a pilot feasibility study, it will not be powered to assess measurable benefit (or lack of) from the yoga program, therefore these outcomes will be exploratory. These outcomes will be collected regardless of the number of yoga sessions attended.

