**Outcome Measures:**

**The study will have the following primary outcome measures:**

- 1- Proportion of adolescent patients with SCD and chronic pain approached that consent to participate in Part A.  
*The study hypothesis is that the proportion of adolescent patients with SCD and chronic pain approached that consent to complete a survey to assess attitudes and practices related to yoga (Part A) will be 50% or greater.*
- 2- Proportion of adolescent patients with SCD and chronic pain enrolled in Part A that consent to participate in Part B.  
*The study hypothesis is that the proportion of adolescent patients with SCD and chronic pain enrolled in Part A that consent to participate in Part B will be 50% or greater.*
- 3- Proportion of participants enrolled in Part B that attend at least 6 of 8 yoga sessions.  
*The study hypothesis is that the proportion of participants enrolled in Part B that attend at least 6 of 8 in-person yoga sessions will be 80 percent or greater.*
- 4- Proportion of participants enrolled in Part B with an ED visit or a hospitalization for pain within 24 hours of completion of each yoga session.

*The study hypothesis is that the proportion of participants enrolled in Part B with an ED visit or a hospitalization for pain within 24 hours of completion of each yoga session will be 30% or less.*

- 5- Proportion of participants in Part B who complete all study assessments.  
*The study hypothesis is that the proportion of participants who complete all study assessments before, and at the end of the yoga program will be 70% or greater.*
- 6- Adherence to submission of pain diary.  
*The study hypothesis is that the proportion of participants who submit at least 4 days of pain diary data before, and at the end of the yoga program will be 70% or greater.*

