#### **Anticipated results and Potential problems, alternate strategies:**

We may encounter difficulties with enrollment of participants. Participants may be uninterested in complementary therapies or may believe that they may not help with chronic pain. They may not want to pursue yoga as a complementary therapy due to concerns that this may be in

conflict with their religious beliefs. There may be cultural barriers to acceptability of yoga. The yoga instructors or investigators, who are familiar with addressing concerns about yoga, will be available to answer any questions they may have about the practice of yoga itself and if potential participants have any concerns regarding yoga as a spiritual practice.

Once enrolled in Part A, participants may not complete survey, though we expect that this non completion rate will be low. Once enrolled on part B, participants may decide not to participate further in the study, or may have a medical complication between enrollment and participation in the yoga sessions that may not allow them to participate in the study. Participants may not attend one or more in-person yoga sessions. We will attempt to determine the causes for individuals dropping out of the program.

There may also be discontinuation of the program due to increased pain, or perceived increased pain, and this will also be noted as a reason for discontinuation. Systematic reviews have not shown increased risk of severe adverse events by the use of yoga in the management of chronic pain syndromes. In addition, there may be changes in health status that may prevent safe continuation of the yoga program. These aims will generate critical data on the feasibility acceptability, reach and maintenance of yoga in adolescents with SCD and chronic pain.

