#### *Withdrawal from Study*

The participant may withdraw from the study at any time by notifying the PI and/or the research team. All data collected up until the point of withdrawal may be included in data analysis. Reason for withdrawal will be noted if provided. No further data will be collected after withdrawal.

*Recruitment of Women and Minorities as Research Subjects:* Majority, if not all, of the patients will be of minority ethnic origin because of the demographics of distribution of SCD. It is possible that more females may be enrolled, as chronic pain is more common in females. The racial, gender and ethnic characteristics of the proposed subject population is expected to reflect the demographics of patients in the CHOA clinic. No exclusion shall be based on race, ethnicity, or gender.

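### One sentence ties the repeat surveys to having attended a session, against Aim 2, so enrollees who stay in the study but attend none cannot complete primary outcome 5

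*Combined protocol and SAP*

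**What the plan says.** Three places in the protocol govern the post-program surveys.

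- **Aim 2, Rationale**, on the health and psychological measures taken before and after the program: "These outcomes will be collected regardless of the number of yoga sessions attended".
- **Part B, Assessments, item 1 (Surveys)** sets only a time window: "up to 4 weeks before the anticipated start of the yoga sessions, and up to 4 weeks after completion of the last yoga session". It states no attendance condition.
- **Part B, Assessments, paragraph after item 7**: "After the sessions have ended, and the participant has attended at least one session, all surveys will be repeated and a qualitative interview" is then conducted.

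Primary outcome 5, under Outcome Measures, is "Proportion of participants in Part B who complete all study assessments". The target set for it reads: "the proportion of participants who complete all study assessments before, and at the end of the yoga program will be 70% or greater". It has no limit by attendance and does not list which assessments count. Part B is planned for up to 20 patients.

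The section on anticipated problems expects missed sessions: "Participants may not attend one or more in-person yoga sessions". The Withdrawal section adds: "No further data will be collected after withdrawal".

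**The concern.** Take an enrollee who has not withdrawn but attends none of the eight sessions. Staff who follow Aim 2 would ask for the post surveys. Staff who follow the paragraph after item 7 would not. Nothing in the protocol says which rule governs.

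The choice affects a primary outcome. Outcome 5 is meant to show whether these measures can be collected in a larger study. If the surveys are never requested from someone who still counts in the denominator, that person is a non-completer by rule, and the outcome mixes feasibility of collection with having attended at least once.

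This does not merely repeat outcome 3. Someone with one to five sessions fails outcome 3 but is still asked for every survey, so only zero-session enrollees are affected. Surveys that were never requested also cannot be recovered at analysis.

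**Working it through.** **Inputs from the protocol.** N = 20, the Part B maximum. The benchmark is 70%, so 0.70 × 20 = 14 completers are needed. The protocol gives no expected number of zero-session enrollees, no completion rate and no sample-size calculation for this outcome, so there is no planned figure to reproduce.

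**Assumed inputs.**
- z: enrollees who attend no session and have not withdrawn.
- q: completion probability among the other N − z.
- r: completion probability among the z if they are asked.

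Completions are taken as independent.

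**Step 1, the ceiling.** If the z are not asked, the most that outcome 5 can reach is (N − z)/N, and the rate needed among the others is 14/(20 − z).

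| z | Ceiling | Rate needed among the others |
|---|---|---|
| 1 | 19/20 = 95% | 14/19 = 73.7% |
| 2 | 18/20 = 90% | 14/18 = 77.8% |
| 3 | 17/20 = 85% | 14/17 = 82.4% |
| 4 | 16/20 = 80% | 14/16 = 87.5% |
| 6 | 14/20 = 70% | 14/14 = 100% |
| 7 | 13/20 = 65% | not reachable |

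The ceiling alone rules out 70% only from z = 7. Because 20 is a maximum, smaller N matters too: N = 15 needs 11 completers (not reachable from z = 5), and N = 10 needs 7 (not reachable from z = 4).

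**Step 2, a plausible range for z.** If outcome 3 meets its target, at least 0.80 × 20 = 16 attend six or more sessions, so at most 4 fall below six and z is at most 4. Reaching z = 4 would need all four of those people to attend nothing and yet stay in the study. It is an upper case.

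**Step 3, chance of reaching the benchmark.** P[Bin(20 − z, q) + Bin(z, r) ≥ 14]. Setting r = 0 represents the z not being asked. At q = 0.85:

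| z | Not asked | Asked, r = 0.10 | r = 0.25 | r = 0.50 |
|---|---|---|---|---|
| 1 | 0.946 | 0.950 | 0.956 | 0.965 |
| 2 | 0.879 | 0.895 | 0.916 | 0.946 |
| 3 | 0.756 | 0.797 | 0.851 | 0.919 |
| 4 | 0.561 | 0.647 | 0.755 | 0.884 |

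**Step 4, sensitivity to q at z = 4** (not asked, then r = 0.10, 0.25, 0.50):
- q = 0.80: 0.352, then 0.447, 0.579, 0.761.
- q = 0.90: 0.789, then 0.841, 0.901, 0.962.

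At z = 1 and q = 0.90 the change is only from 0.991 to 0.995 at r = 0.50.

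**The case against.** **The sentence may be only a summary.** The paragraph after item 7 has no word such as only, refers back to the items above it, and also covers the interview, whose questions on perceived benefit and risk presuppose attendance. Aim 2 is the express rule and could be taken to govern. Alternatively, Aim 2 could mean any attendance from one session upward, which removes the contradiction. Both readings are possible, but neither is stated. The second leaves the ceiling in place, because zero-session enrollees would still go unasked and still be counted.

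**Some zero-session enrollees will have withdrawn.** The section on anticipated problems includes people who stop taking part, or who have a medical complication before the sessions start. Where these are withdrawals, data collection ends under either rule. This stands: withdrawals lower the ceiling whichever rule applies, so z here counts only people still in the study.

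**The large figures come from an upper case.** This also stands. At z = 1 the effect is negligible to small.

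**The analysis is descriptive.** The Analytic Methods section plans descriptive statistics and ties no formal decision to 70%. Reporting z with the numerator and denominator would help a reader, but would not replace surveys that were never requested.

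**A reader might infer that the denominator is open**, so that the 70% verdict could be changed by counting attenders only. The documents do not support this. Outcome 5 refers to participants in Part B without an attendance limit, and nothing proposes an attenders-only version.

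**Conclusion.** The point holds, at moderate weight. The protocol gives two unreconciled instructions for post surveys in zero-session enrollees who remain in the study. Following the paragraph after item 7 caps primary outcome 5 at (N − z)/N.

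At N = 20 and q = 0.85, not asking these people lowers the chance of reaching 14 of 20 by 0.965 − 0.946 = 0.019 at z = 1 with r = 0.50. At z = 4 the loss is between 0.647 − 0.561 = 0.086 (r = 0.10) and 0.884 − 0.561 = 0.323 (r = 0.50). The values of z, q and r are assumptions. The ceiling itself rests only on the stated denominator.

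A reader might infer that the clause puts the 70% hypothesis out of reach. It does not unless z is at least 7 of 20, and z cannot exceed 4 if the attendance target is met. Nor is the clause a defect for the other assessments: its attendance condition does not cover the pain diary, which has its own outcome 6, and limiting the interview to attenders does not conflict with Aim 2, because the interview belongs to Aim 3.

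**What to change.** 1. In the paragraph after item 7, remove the attendance condition for the repeat surveys, so that it agrees with Aim 2 and with item 1. It may stay for the interview.
2. For someone with no sessions, count the four-week window from the last scheduled session of that person's group. This needs saying because the "study cohort may be split into 2 or more groups".
3. Keep all Part B enrollees as the denominator of outcome 5, and state that a missing interview does not count against a zero-session enrollee who was not eligible for it. Item 2 lists the interview among the assessments, so without this the ceiling would return through the interview.

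The cost is a few sentences and a few extra telephone contacts, which item 1 already permits. At z = 4 the post-survey payments come to at most 4 × $25 = $100, already within the planned maximum of $303 per Part B participant. The downside is that some of these enrollees will not respond, so the gain may be nearer the r = 0.10 column than the r = 0.50 column.

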Lack of awareness and access to yoga are barriers to the use of yoga, and smartphone apps may overcome this barrier. Limited health knowledge is one of the reasons for non-use of complementary therapies, and individuals with lower educational attainment, and lower income were more likely to report lack of knowledge as a reason for non-use of these therapies. There are increased challenges in access to yoga for minority and low-income populations, since yoga is often a fee-based service and there may be additional limitations due to geographical access.

While there is currently no data on the use of yoga as a Complementary and Alternative Medicine (CAM) therapy in SCD chronic pain, one study in acute SCD pain suggest that the practice was well accepted and well tolerated. Additionally, preliminary data from a secondary data analyses of the decision aid study suggests that adult patients express a desire for non-medication based pain relief. These data indicate that patients with SCD who suffer from chronic pain, may be willing to consider CAM therapies. A customized yoga program, taking into account risks of SCD, and limitations posed by SCD-related comorbidities, including but not limited to fixed deformities, AVN, splenomegaly, lung disease, cerebral vasculopathy, retinopathy, etc.

The overarching goal of this study is to 1) determine the acceptability of yoga for chronic pain in SCD 2) determine the feasibility of a yoga program for individuals with SCD chronic pain, 3) determine the safety of a yoga program for individuals with SCD chronic pain, 4) determine the feasibility of collection of psychological and patient reported outcomes in a study of yoga for chronic pain and 5) Explore patient acceptability of yoga through qualitative interviews and conduct a needs assessment for the development of a smartphone app for yoga.

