**Hypothesis:** 2a) We hypothesize that 70% or more of participants will complete all study assessments before, and at the end of the yoga program. 2b) We hypothesized that the proportion of participants who submit at least 4 days of pain diary data before, and at the end of the yoga program will be 70% or greater.

**Aim 3. Explore patient acceptability of yoga through qualitative interviews and conduct a needs assessment for the development of a smartphone app for yoga.**

**Rationale:** Qualitative Interviews will be used to assess aspects of acceptability and use of yoga as an adjunct therapy for SCD chronic pain. We will also use qualitative interviews format to assess participant interest and perceived needs in the development of a smartphone yoga app. Qualitative thematic analysis methods or other methods as applicable will be utilized.

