We will also obtain demographic information including but not limited to age, sex, race, ethnicity, family income, insurance status, parent and child education status, family composition and parent marital status, religious affiliation, availability of transportation and distance from the

proposed yoga site. If participants indicate they have previously practiced yoga, we will also gather the following: when yoga was first practiced, number of months/years' yoga has been practiced, frequency of practice and time of most recent practice of yoga. For Group 1 participants, this form may be completed by the parent/guardian for those <18, and by the participant if >18, with or without assistance from the research coordinator. For Group 2 (parent) participants, this will be completed by the parent themselves, with or without assistance from the research coordinator.

At the end of Part A, Group 1 participants will be asked if they are interested in learning about participating a study of yoga for chronic SCD pain. If they answer yes, then they will learn more about the proposed program, and Part B of the study will be offered to them. In addition to the research coordinator discussing the Part B yoga program, we will use written materials to help participants become familiar with what they may expect in part B (attached with this protocol), which will include pictures of sample yoga and breathing routines. Participants may take the Part B consent form with them to think over if they wish to consider this prior to enrolling or refusing participation in Part B. If participants are not interested in a pilot study of yoga or do not wish to enroll/are unable to enroll on Part B, investigators will request and document reason for refusal (if provided), and participant will not have to complete additional study procedures. The proportion of those who complete Part A but do not wish to consent for Part B will be recorded. Group 2 participants will not be offered Part B.

It is anticipated that this introduction and pictures for part B will take approximately 10-15 minutes.

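### As described, Aim 3 asks about the smartphone app only of Part B participants who attended at least one session, which limits whom its findings apply to

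*Combined protocol and SAP*

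**What the plan says.** The Aim 3 rationale uses qualitative interviews to "assess participant interest and perceived needs in the development of a smartphone yoga app". Item 2 of the Part B Assessments puts this into a single interview after the program: "We will also use qualitative interviews format to assess participant interest and perceived needs in the development of a smartphone yoga app". The same interview covers "challenges, barriers to successful participation, feedback on yoga classes and content, and other related themes".

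The paragraph that follows item 7 sets the condition. It applies once the sessions are over and "the participant has attended at least one session, all surveys will be repeated and a qualitative interview will be conducted", and it lists acceptability and perceived benefits and risks "as well as the perceived needs in the design of a smart-phone accessible yoga app; as described above".

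On the reason for an app, Background and Significance says: "Lack of awareness and access to yoga are barriers to the use of yoga, and smartphone apps may overcome this barrier". It then names fees and geography as limits on access.

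Part A patients who are not interested in Part B, or cannot join it, are asked why. The reason is recorded if they give one, and beyond that the "participant will not have to complete additional study procedures". The rationale for Aim 2 says its pre- and post-program outcomes are gathered irrespective of how many sessions a participant attended.

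**The concern.** An app is proposed partly because some patients cannot get to classes, yet the only described source of app data is patients who got to at least one. Three steps come before the interview: interest in hearing about a yoga study, consent to in-person sessions, and attendance. Two groups drop out along the way. One is Part A patients who decline or cannot join Part B. The other is Part B enrollees who attend nothing. Both may include patients for whom distance, time or transport was decisive.

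If their needs or preferred format differ from those of attenders, Aim 3 will not show it. The Analytic Methods section also expects the qualitative work to speak to wider issues of acceptability and to barriers to use, which is more than attenders alone can describe.

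**Working it through.** **Who can reach the app questions, as described**

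| Group | Data described | App needs covered? |
|---|---|---|
| Part B, attended at least one session | Post-program surveys and interview | Yes |
| Part B, attended none | Baseline data; optional staff follow-up on missed sessions; causes of dropout sought | Not described |
| Part A only | Attitudes survey, questionnaires, income, transport and distance; refusal reason if given | Not described |

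**Inputs.** Part A Group 1 maximum A = 40 and Part B maximum B = 20, with Part A recruitment ending when 20 have joined Part B (Total number of participants). Hypothesised consent from Part A to Part B is at least 50%, and hypothesised attendance at 6 or more of 8 sessions is at least 80% (Outcome Measures 2 and 3). The number of enrollees who attend no session, z, is not given and is treated as an assumption.

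**The plan's own figure.** 40 × 0.50 = 20, so the two maxima agree with the consent hypothesis.

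**Loss from placing Aim 3 inside Part B.** With 20 in Part B and z = 0, the number not interviewed is A − 20:

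| Part A size when 20 have joined Part B | Not interviewed | Share |
|---|---|---|
| 20 | 0 | 0% |
| 25 | 5 | 20% |
| 30 | 10 | 33% |
| 40 | 20 | 50% |

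Under the plan's consent hypothesis, 20 of 40 is the largest loss from this step. It would be larger if Part A filled and fewer than 20 joined Part B.

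**Added loss from the one-session condition.** If exactly 80% of 20 meet the attendance target, 16 do and 4 fall short. Those 4 may have attended from 0 to 5 sessions, so z lies between 0 and 4. Interview coverage of a full Part A is (20 − z)/40:

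- z = 0: 20/40 = 50% interviewed, 20 missed.
- z = 4: 16/40 = 40% interviewed, 24 missed.

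**How likely the condition is to exclude anyone.** If each enrollee independently has probability p of attending nothing, the chance of at least one such person among 20 is 1 − (1 − p)^20. For assumed p of 5%, 10% and 20% this is 64%, 88% and 99%.

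**The conflict on surveys.** The Aim 2 rationale collects the pre- and post-program outcomes regardless of attendance, while the closing paragraph of the Assessments section repeats the surveys only after at least one session. Under that paragraph a non-attender cannot complete the post-program surveys. The ceiling on primary outcome 5 (all assessments completed, target 70%) then becomes (20 − z)/20, which is 16/20 = 80% at z = 4.

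**The case against.** The strongest reply has four parts.

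- **The app has other purposes.** The Abstract says existing apps are not tailored to sickle cell pain, Background also cites lack of awareness, and the Aim 1 rationale says customised content is not available to patients. People who have tried the routines are well placed to say what a tailored app should contain. This stands.
- **Attenders can still have poor access.** The sessions are run by the study, scheduled around participants, and supported by $25 each for transport and parking. A reader might infer that everyone interviewed has overcome the access barrier, is the wrong group to ask, and leaves Aim 3 unable to guide the app. The documents do not support that. A low-access patient who came once is interviewed, and coming to a subsidised class does not show access to ordinary yoga.
- **Barriers are also recorded elsewhere.** Income, transport, distance, refusal reasons, optional follow-up of missed sessions, causes of dropout, and analyses of predictors of acceptability and attendance all bear on them. So it would be wrong to say that barriers go unrecorded outside the interview. None of these sources, however, is described as covering app needs.
- **The Part A survey and interview script are attachments not available here.** App items in the Part A survey cannot be ruled out. The text describes that survey as covering attitudes, practices and acceptability of yoga, and the one-session condition stands whatever the attachments contain.

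The condition is also natural for an interview largely about experience of the program, and it causes less of the loss than the placement of Aim 3 in Part B. Both points are right, and they shape the fix.

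**Conclusion.** The point holds as a limit on whom the exploratory Aim 3 findings apply to. With Part A full and 20 in Part B, 20 of 40 patients are not asked about the app. The number is smaller if Part A stops early, down to none if all of the first 20 join. The one-session condition removes a further 0 to 4 enrollees if the attendance target is just met, and more if it is missed.

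This rests on the described procedures being complete, that is, on the attached Part A survey having no app items, and on assumed values of z. It should not be turned into a bias in an estimated level of app interest. Aim 3 is thematic work, and app interest is neither a primary nor an exploratory outcome, so no proportion is planned.

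The selection does not alter the six primary proportions. The separate conflict over repeat surveys does bear on primary outcome 5 and needs resolving in any case.

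**What to change.** 1. In the closing paragraph of the Part B Assessments section, delete the one-session condition. Offer the post-program surveys and the telephone or in-person interview to every Part B enrollee who has not withdrawn, and skip the experience questions for those who attended none. This also removes the conflict with the Aim 2 rationale.
2. Unless the attached Part A survey already has them, add a few items for Group 1 on app interest, device access and preferred format. Step 1 alone would still reach at most 20 of 40 when Part A fills; with these items, up to 40 of 40 could contribute.
3. Report app and barrier findings separately for attenders, non-attending enrollees and decliners.

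The cost is a slightly longer Part A survey and at most a few more interviews of 20 to 30 minutes. The $25 interview payment and the $25 post-program survey payment are already listed for each Part B participant. For z = 4 that is 4 × $50 = $200, within the existing per-participant maximum. The yoga program itself does not change.
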